Pre-treatment Research Assessment (Time 1 [T1]) takes place ~2 weeks prior to group-treatment start. Parent questionnaires are reviewed by a Clinical Research Project Coordinator (CRPC) to ensure completion. The CRPC administers the ADIS-P with the parent and then completes the '10 Steps to Talking' with the child in the presence of the parent (video-recorded). The only speech and language assessment completed as part of the study is conducted (and video-recorded) at this T1 visit. Upon completion of the T1 visit, the CRPC **randomly assigns** each eligible child and parent to either the (1) "*Taming Sneaky Fears for SAD and/or SM*" parent and child group CBT program or (2) the "*Parent Psycho-education and Child Socialization*" group program, and informs them of group assignment. The online software *Sealed Envelope*TM (<https://www.sealedenvelope.com/>) is used to randomize. This program is commonly used by hospital research studies because it uses computer-generated sequences to allocate participants to each group. Allocation of participants uses sealed, opaque envelopes and remains concealed until study completion. The CRPC and lead child group and parent group therapists ([name]) are not blinded, however, the clinicians completing the post-intervention (T2) and 6-month follow up (T3) assessments are blind to treatment type, previous ratings on all measures, and time of assessment.

Implementation of Treatment Protocols: Both group treatment protocols run concurrently, but on different days. A total of 5 “*Taming Sneaky Fears*” and 5 “*Parent Psycho-education and Child Socialization*” groups need to run over the course of the 2-year study with 8 - 9 children per group (total of 40 - 45 children per treatment arm over study period). Groups run weekly for 1 hour for nearly 3 months (10 + 1 sessions) starting in September 2015, October 2015, November 2015, March 2016, and April 2016. As the final treatment groups for the study are completed by mid-July 2016, the final 6-month follow-up takes place in mid-January 2017, prior to the end of the study (see Time line of Study p. 10). Regardless of the treatment program, the first treatment visit is for parents only at which time parents are introduced to the therapists and other parents in the group and provided a copy of the “*Parent Manual*” relevant for each group (either the Parent Manual for “*Taming Sneaky Fears for SAD and SM*” or the one for “*Parent Psycho-education and Child Socialization*” that includes handouts provided as part of the “*Improving Parent-Child Relationship*” series of videotapes).

In both treatment protocols, parents and children attend weekly, 1-hour group sessions for 10 consecutive weeks at HSC. In order for the 2 treatments to be comparable, each child group follows the same format, i.e., starts with a ‘review of the week’, followed by a story then craft activity and ends with a snack. At the end of each session, a child therapist drops into the parent group to inform parents about strategies and activities taught to children that day (typically, a 30-second general summary). At the mid-point of both group treatments, a child therapist meets with parent(s) individually to discuss their child’s progress. Therefore, children in both treatments receive equal opportunities for interaction with therapists and socialization with peers with the only difference between groups being that children in the “*Taming Sneaky Fears for SAD and/or SM*” group receive CBT while the children in the comparison group do not. Similarly, both parent groups start with a review of homework, then new information is provided and finally, homework is assigned; with the main difference between groups being that in “*Taming Sneaky Fears for SAD and/or SM*” parents receive CBT.

A. “*Taming Sneaky Fears*” Child and Parent Group CBT Protocol: Both children and parents separately, but concurrently, receive CBT in a group format. Using stories, games, and puppets, children are taught a variety of CBT strategies to manage anxiety, especially social anxiety and mutism (e.g., ‘use your voice’), and socialization and interaction with peers and group leaders are encouraged. Parents are taught CBT strategies with a strong emphasis on building hierarchies (progressive desensitization) for speech and social situations.

B. “*Parent Psycho-education and Child Socialization*” Protocol: The parent component of this protocol is made up of a variety of psycho-educational topics, for example, parenting, child behaviour, nutrition, sleep, and normative development. A series of psycho-educational videotapes developed for parents with accompanying parent information handouts (www.improvedparenting.com) is used. Parents view two 30-minute videotapes from the series at each session. In the child group, children listen to stories, play games, complete crafts and have opportunities to interact and socialize with peers and group leaders. Therapists encourage socialization, manage behaviours and interact with children to parallel the “*Taming Sneaky Fears for SAD and/or SM*” group.

Post-group Research Assessment (T2) and Longer-term (6-month) Post-group Research Follow-up (T3): Each post-treatment research visit takes ~2½ hours to complete, is video-taped and is similar to the T1 visit except there is no speech and language assessment. To ensure an unbiased assessment and clinician rating of the ADIS (-P and -CSR) and CGAS, a psychiatrist or graduate (PhD) student trained in the ADIS and blinded to treatment group, previous ratings, and time of assessment, administers the ADIS-P to the parents. This assessor then conducts the “10 Steps to Talking” protocol with the child in the presence of the parent. Parents also complete the same questionnaires used at T1, with the addition of one new questionnaire (the SWAN Rating scale). Parents are provided with teacher questionnaires prior to the end of treatment and bring them back (completed by teachers) at T2, while teacher questionnaires are mailed out to parents a few weeks prior to the 6-month post-intervention (T3) assessment and parents bring the completed questionnaires at the T3 visit. Teacher questionnaires are completed by teachers who know the child well as close to the assessment time as possible (e.g. if a research assessment is in July, the teacher completes the questionnaire prior to the end of school year).

Children receive stickers and parents are reimbursed \$20.00 to compensate for expenses such as parking and/or other expenses incurred because of participation in the research assessments at each of the T1, T2, T3 assessments. The 3 research assessments are video-recorded and ≥5% of randomly assigned recordings are reviewed by all assessors (coordinators + assessors at T2 and T3) to establish inter-rater

reliability on ADIS-CSR and CGAS. We acknowledge the difficulty in following families after treatment and to encourage subject retention, 1 of the coordinators contacts families by phone 3 months post-treatment and the need for ongoing monitoring and follow-up to maintain gains made is emphasized to parents.

Statistical Analysis and Data Analyses Plan:

Data for demographic variables will be summarized using counts, percentages, measures of central tendency (average, median, mode) and measures of sample variation (standard deviation, range).

Parametric statistics (average, standard deviation) will be used for interval and ratio data.

[figure not shown]
To address Hypothesis 1, we will use a two-sided Chi-Square test with continuity correction to compare the difference between the two 2 groups in the proportion of children who lost diagnoses post-treatment (T2) and 6 months post-treatment (T3).

To test Hypothesis 2, we will use a repeated measures regression model on the ADIS-CSR and compare the two 2 treatment groups from pre-treatment (T1) to 6-month post treatment (T3). An interaction term between time and group will be introduced in the model in order to explore possible differences at different time points between the two groups. The assumptions of the model will be verified using residual analysis and, if necessary, transformations will be used in order to obtain a valid model. This repeated measures regression model will be used for Hypotheses 3 and 4 to assess child global functioning using CGAS and parent and teacher reports of child symptoms on SMQ, SASC-P/T and SSQ.

To examine Hypothesis 5, a logistic regression analysis will be employed. This will allow for the examination of the strength of multiple predictors on the likelihood that a child will lose an anxiety disorder diagnosis 6 months post-intervention (T3). The predictor factors that will be included in this model include group intervention (“*Taming Sneaky Fears for SAD and/or SM*” or “Parent Psycho-education and Child Socialization”), within-the-child factors (child’s age, sex, BI, and speech-language difficulties), parent factors (family history of SAD or SM), and environmental factors (family stress, immigration status). All the significant factors will be put into the model and non-significant predictors will be excluded. The model will control for age and sex of the child.

ORIGINALITY AND SIGNIFICANCE/RELEVANCE: This is the first RCT to assess the efficacy of “*Taming Sneaky Fears for SAD and/or SM*”, a group CBT treatment approach to treat 4 to 7 year old children with SM and/or SAD, which are anxiety disorders affecting as many as 36,340 children under age 14 in Ontario. The present study addresses methodological shortcomings of previous studies and builds on OMHF-funded previous work while addressing a significant clinical problem for which little convincing evidence for treatment efficacy exists. The present study represents an innovative treatment method that is brief, CBT-based, and group-focused.

Timeline of the Study:

REFERENCES

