RESEARCH QUESTIONS AND HYPOTHESES TO BE TESTED: This study builds on our previous OMHF funded work in which we demonstrated that 5 to 7 year old children with anxiety disorders randomized to the “*Taming Sneaky Fears*” group CBT program exhibited greater improvements in global functioning and lost more diagnoses than those randomized to the parent only group CBT program. Starting with a previously proven treatment protocol that is engaging and teaches young children various CBT strategies, we use a slightly revised and refined treatment protocol specifically for children with SAD and/or SM and their parents and expand the age range down to 4 years. The primary objective of this study is to assess the efficacy of the brief (10 concurrent parent and child + 1 parent only), refined, group CBT program “*Taming Sneaky Fears for SAD and/or SM*” in the treatment of 4 to 7 year old children with SAD and/or SM.

Hypothesis #1: The “*Taming Sneaky Fears for SAD and/or SM*” group CBT treatment is more efficacious than a comparison intervention, “Parent Psycho-education and Child Socialization” such that more children in the “*Taming Sneaky Fears for SAD and SM*” group CBT will lose their primary diagnosis of SAD and/or SM, compared to children in the comparison group. Our primary outcome measure will be loss of diagnosis of SAD and/or SM as assessed by an independent clinician blinded to treatment condition and time of assessment using a semi-structured interview, the Anxiety Disorders Interview Schedule for Parents [ADIS-P]),⁵⁹ post-intervention and at 6-month follow-up.

Hypothesis #2: In those children who do not lose their primary diagnosis of SAD and/or SM, there will be a 2.0 or greater point improvement in anxiety severity (measured by an independent assessor blinded to treatment condition and time of assessment, using the ADIS-P Clinical Severity Rating [ADIS-CSR]) in more children in the “*Taming Sneaky Fears for SAD and/or SM*” program than children in the comparison group at post-intervention and at 6-month follow-up. This hypothesis is based upon a recent meta-analysis that suggests a 2.0 change in the ADIS-CSR is a clinical meaningful change.⁶¹

Hypothesis #3: In those children who do not lose their primary diagnosis of SAD and/or SM, there will be a 10.0 or greater point improvement in global functioning (measured by an independent assessor

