blinded to treatment condition and time of assessment, using the Clinician Global Assessment Scale [CGAS]⁶¹ in more children in the “*Taming Sneaky Fears for SAD and/or SM*” than children in the comparison group at post-intervention and at 6-month follow-up. A ≥10 point change means change from one category to the next on the CGAS.

A second objective of this study is to evaluate parent and teacher ratings of child symptomatology (SAD and SM) at home and in the classroom, respectively, over the course of the treatment program.

Hypothesis #4: Parents of children who attend the “*Taming Sneaky Fears for SAD and/or SM*” will report significantly fewer symptoms over the course of the study than those in the “Parent Psycho-education and Child Socialization” as measured by the parent Selective Mutism Questionnaire (SMQ)⁶² and the Social Anxiety Scale for Children Revised for Parents (SASC-P).⁶³ Similarly, teachers will report significantly fewer symptoms over the course of this study in children who attend the “*Taming Sneaky Fears for SAD and/or SM*” than those in the “Parent Psycho-education and Child Socialization,” as measured by the teacher School Speech Questionnaire (SSQ)⁶⁴ and the Social Anxiety Scale for Children Revised for Teachers (SASC-T).⁶³

A third objective is to explore factors within the child, parent and environment that predict treatment outcome (i.e., loss of at least one anxiety diagnosis post-treatment; this objective could not be explored in the original OMHF study due to the small sample size and lack of power). Factors hypothesized to predict treatment outcomes include within-the-child factors (age, gender, BI, and speech-language difficulties) and within-the-parent/environment factors (family history of SAD or SM, immigration status, and family stresses).

Hypothesis #5: The most significant factor to predict treatment outcome (i.e. lost diagnosis) at 6 months will be treatment group. The other factors (age, gender, BI, speech-language difficulties, family history of SAD or SM, immigrations status, family stresses) will not be significant in predicting treatment outcome.

METHODS:

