Sample Size Calculation is based on data from our previous OMHF study, showing that 42% of children in the “*Taming Sneaky Fears*” program lost their primary diagnosis of SAD and/or SM post-intervention vs. none of the children in the comparison group (using the ADIS-P). In the present study, we conservatively estimate that 10% of children will lose their SAD and/or SM diagnosis in the comparison group. Hence using this difference of 32% (42% - 10%), a sample size of 69 (to round up, 35 subjects per treatment protocol) would achieve a power of 81% to detect a difference of 32% between treatment programs using a two-sided Chi-squared test with continuity correction with a significance level set at 0.05.⁶⁵ Further, a total of 15/77 children (19%) did not complete the full protocol in the original OMHF study, so we anticipate a 20% (n=18) dropout rate over the course of this study. As a result, 88 participants need to be recruited to ensure a final sample size of 70. In order to obtain a sample size of 88

participants over two years, 2 sites are necessary.

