Recruitment: Children referred for an assessment of SAD and/or SM at either site are assessed by 1 of the 4 child psychiatrists, who obtains information about presenting problem, its impact on the child's functioning at school, home and with peers, and developmental, medical and family history. Eligible, interested children and families meet with a Clinical Research Project Coordinator (coordinator) who describes the study immediately post-assessment at either HSC or TEGH (depending on site where child was assessed). The coordinator obtains informed consent from parent(s) and assent from child, gives pre-treatment questionnaires to the parent(s), and schedules the first research assessment visit (Time 1) at HSC within 2 to 3 weeks of assessment and start of treatment group. Children and families not eligible for the study or who decline to participate are treated or referred for appropriate treatment as usually done in each clinic.

Measures: A demographic questionnaire (child's age and gender, parent's name, family composition, family history of SAD or SM, and immigration status) is completed by the parent at the start of the study.

A. Clinician Rated Measures:

- 1) The Anxiety Disorders Interview Schedule for DSM-IV, Parent Version (ADIS-P)⁵⁹ is used to assess SAD and/or SM. The ADIS-P has good reliability,⁶⁶ is sensitive to treatment effects in child anxiety studies,^{66,67} and has been used in a number of studies on preschoolers^{45,46,48} and SM treatment.⁵⁸ Clinical Severity Rating (ADIS-CSR) uses a 0 to 8 scale to measure clinical severity of diagnosis; a CSR of ≥ 4 indicates clinically significant symptoms and presence of an anxiety disorder. A trained independent clinician blinded to treatment type and time of assessment completes the CSR.
- 2) The Children's Global Assessment Scale (CGAS)⁶¹ assesses adaptive functioning during the previous month for children aged 4-16 years. It has high inter-rater and test-retest reliability. A trained independent clinician blinded to treatment type and time of assessment completes the CGAS.

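### Hypotheses 2 and 3 compare responders only among children who keep the diagnosis, but the planned model has no responder variable and no stated analysis set

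*Combined protocol and SAP*

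**What the plan says.** Under Research Questions and Hypotheses to be Tested, Hypothesis 1 sets the primary endpoint: "Our primary outcome measure will be loss of diagnosis of SAD and/or SM", judged by a blinded clinician after the intervention (T2) and at 6 months (T3).

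Hypothesis 2 then restricts attention to children without that success: "In those children who do not lose their primary diagnosis of SAD and/or SM, there will be a 2.0 or greater point improvement" on the ADIS-CSR, in more CBT children than comparison children, at both visits. Hypothesis 3 applies the same restriction to the CGAS: "there will be a 10.0 or greater point improvement in global functioning". The plan justifies that threshold as follows: "A ≥10 point change means change from one category to the next on the CGAS".

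The Statistical Analysis and Data Analyses Plan describes something different. For Hypothesis 2, "we will use a repeated measures regression model on the ADIS-CSR", from T1 to T3, with a group-by-time interaction, residual checks and transformations if needed. For the next hypotheses, "This repeated measures regression model will be used for Hypotheses 3 and 4 to assess child global functioning using CGAS". That section has no 2-point or 10-point variable and no restriction to children who keep the diagnosis. It does not say who is analysed.

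**The concern.** The hypotheses and the analysis differ in two ways: the endpoint (reaching a threshold versus a score over time) and the population (children who keep the diagnosis versus unstated).

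The population matters more. If treatment works as Hypothesis 1 predicts, it changes who is left in the subset. The two retained groups are then no longer comparable by design, and a difference between them can arise with no treatment effect on anyone in the subset. The text also does not say whether a child counts as keeping the diagnosis by status at T2, at T3 or at each visit. This matters because the Feasibility section reports six further children losing the diagnosis between post-treatment and 6 months in the earlier study.

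At stake is the interpretation of the two secondary clinician-rated results, and the risk that the analysis set is settled after the data are seen.

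**Working it through.** **Inputs.** Sample Size Calculation: 42% (CBT) and 10% (comparison) lose the diagnosis at T2; 35 per arm; two-sided 0.05; continuity-corrected chi-square. On the comparison rate the plan says "we conservatively estimate that 10% of children will lose their SAD and/or SM diagnosis in the comparison group". Feasibility of the Study: 10/24 lost the diagnosis after treatment and 6 more by 6 months, so 16/24 = 67% under CBT. Measures: "a CSR of ≥ 4 indicates clinically significant symptoms and presence of an anxiety disorder", on a 0 to 8 scale.

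**The plan's own figure.** The continuity-corrected formula for 42% vs 10% gives 35 per arm and power 0.811, matching the stated 81%. No stated figure is wrong. No other hypothesis is sized.

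**Retained children at T2.** CBT: 35 × (1 − 0.42) = 20.3. Comparison: 35 × (1 − 0.10) = 31.5.

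**How different the subsets are.** The proportion who would keep the diagnosis under comparison but lose it under CBT is at least 0.42 − 0.10 = 0.32. Among retained comparison children this is at least 0.32/0.90 = 0.356, or 36%. The bound needs only the two marginal rates.

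**Size of a spurious difference.** Assume CBT has no effect on children who keep the diagnosis under either arm, and that no child keeps it only because of CBT. Let p be the responder rate in children who keep it under both arms. Let q be the rate, under comparison, in those CBT would have removed.
- CBT retained rate = p
- Comparison retained rate = (0.58/0.90)p + (0.32/0.90)q
- Difference = 0.356 × (p − q)

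The difference is zero if p = q. It is 0.356 × 0.20 = 0.071, about 7 percentage points in either direction, if p and q differ by 20 points. It cannot exceed 36 points.

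**T3.** The comparison rate at 6 months is not given. With CBT loss of 16/24 and an assumed comparison loss c, the share is at least (0.667 − c)/(1 − c):

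| Assumed c | Minimum share |
|---|---|
| 10% | 63% |
| 20% | 58% |
| 30% | 52% |
| 40% | 44% |

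Retained CBT children: 35 × (1 − 16/24) = 11.7.

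**Precision if the hypotheses were tested as worded.** The plan names no responder test for Hypotheses 2 and 3, so this borrows the test of Hypothesis 1. Exact binomial power was computed in 1-point steps, with assumed comparison responder rates. The smallest difference reaching 80% power is:

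| Comparison responder rate | 20 vs 32 | 35 vs 35 |
|---|---|---|
| 10% | 39 points | 31 points |
| 20% | 42 points | 35 points |
| 30% | 43 points | 37 points |

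As a check, the same method gives 83% for 42% vs 10% at 35 per arm, against the plan's 81%.

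**A floor for Hypothesis 2 only.** Suppose keeping the diagnosis means a CSR of at least 4 for that disorder. A child entering at 4 can then improve by at most 4 − 4 = 0 points while staying in the subset, and one entering at 5 by at most 5 − 4 = 1. Only children entering at 6 or more could be responders, and a child going from 5 to 3 leaves the subset as a Hypothesis 1 success. The documents do not define loss of diagnosis by CSR and do not give the share entering at 4 or 5. No such floor applies to the CGAS.

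**Illustration.** A simulation used that same definition and was set to give 42% and 10% loss, with three assumed entry CSR distributions and an assumed SD of change from 1.0 to 2.0. The responder difference was 0.40 to 0.57 in all children and 0.18 to 0.52 among those keeping the diagnosis. Mean entry CSR among the latter was 0.2 to 0.4 points higher in the CBT arm. The two analyses estimate different quantities.

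**The case against.** The strongest reply is that the analysis section compares the two treatment groups without restriction and uses the same model for Hypothesis 4, which has no subset. A set that changes between T2 and T3 could not be fitted in one T1 to T3 model without a rule that the plan lacks. The natural reading is therefore all children with data, where the selection problem does not arise. That may well be what was meant. But then the model does not test Hypotheses 2 and 3 as worded, and the wording has to change. Silence on the analysis set does not settle it.

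Other points stand as qualifications:
- The 67% at 6 months is described as a total and may be cumulative rather than status at that visit. If CBT loss were 50% to 60% (assumed), the share at a 10% comparison rate would be (0.50 − 0.10)/0.90 = 44% to (0.60 − 0.10)/0.90 = 56%, not 63%.
- The precision figures describe a test that the plan does not specify for these hypotheses.
- The CSR floor depends on a definition that the plan does not give, and entry is by psychiatrist's diagnosis rather than a CSR cut.
- A responder comparison in all randomised children needs a rule for missing scores, with 20% dropout expected, and a stated rank against the model.

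None of these removes the mismatch.

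**Conclusion.** The concern holds. The stated hypotheses and the stated analysis differ in endpoint, and the analysis set is not given. One reading leaves the hypotheses untested as worded. The other gives up the protection of randomisation.

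The bound of at least 36% at T2 rests only on the plan's assumed 42% and 10%. The bias of 0.356 × (p − q) also needs the two assumptions stated with it. Its direction is unknown, and no bias is shown to have a particular size. The T3 figures rest on an assumed comparison rate and on reading 67% as status at 6 months.

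This should be fixed, but it does not threaten the trial's main conclusion: Hypothesis 1, its test and its sample size are unaffected.

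**What to change.** In Hypotheses 2 and 3, delete the opening clause that limits them to children who keep the primary diagnosis. Define each as the between-arm difference at T2 and at T3, in ADIS-CSR for Hypothesis 2 and in CGAS for Hypothesis 3, from the planned group-by-time model with T1 as baseline.

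Add to the Statistical Analysis and Data Analyses Plan: *Analysis set for Hypotheses 2 and 3: all randomised children by assigned arm, whether or not the diagnosis is lost.*

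If the 2-point and 10-point thresholds are to be kept, add a comparison of the proportions reaching them among all randomised children. State how missing T2 and T3 scores are handled, and that this comparison supports the model result. Report children who keep the diagnosis descriptively, without a test.

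The cost is the wording of two hypotheses and one analysis paragraph. No new data, visits or sample size are needed.

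### The primary test of Hypothesis 1 has no all-randomised analysis set and no missing-outcome rule, so by default it uses only children with data and is open to selective dropout

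*Combined protocol and SAP*

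**What the plan says.** Under METHODS, Sample Size Calculation, the plan assumes 42% of the CBT arm will lose the diagnosis and, for the other arm, "we conservatively estimate that 10% of children will lose their SAD and/or SM diagnosis in the comparison group". It finds that "a sample size of 69 (to round up, 35 subjects per treatment protocol) would achieve a power of 81" per cent, "using a two-sided Chi-squared test with continuity correction with a significance level set at 0.05".

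The allowance for dropout comes from 15 of 77 children (19%) who "did not complete the full protocol in the original OMHF study". This is rounded to 20% (n=18) over the course of the study, so "88 participants need to be recruited to ensure a final sample size of 70". The Sites section again treats 70 as the minimum number to retain.

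Under Statistical Analysis and Data Analyses Plan, Hypothesis 1 is tested by the same chi-square, comparing the arms "in the proportion of children who lost diagnoses post-treatment (T2) and 6 months post-treatment (T3". That section does not say which children are analysed, what happens to a child without a T2 or T3 ADIS-P, or whether any sensitivity analysis is planned. The section on the T2 and T3 assessments describes a telephone call three months after treatment and a payment at each assessment. It does not say whether a child who has stopped attending sessions is still assessed.

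**The concern.** A chi-square on loss of diagnosis needs an outcome for every child it counts. With no rule for missing outcomes, the natural reading is that children without a T2 or T3 interview leave the comparison. The only analysed number in the plan, 70, fits that reading. About a fifth of the children could then be absent from the primary result, and the arms compared would no longer be the arms randomised.

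Selective dropout is plausible. Families are told their assignment after T1 and are asked to attend 11 weekly sessions and three research visits over nine months. The comparison programme contains no CBT. If the children who leave differ in outcome, and differ by arm, the comparison among those remaining can create a difference or hide one. Leaving the rule open also allows the analysis set to be chosen after the results are known.

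**Working it through.** **1. The plan's own figures.** Inputs from the sample size section: p1 = 0.42, p2 = 0.10, difference 0.32, mean 0.26, two-sided 0.05, continuity correction.

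- Uncorrected n per arm at 81% power: (1.960·√(2·0.26·0.74) + 0.878·√(0.42·0.58 + 0.10·0.90))² / 0.32² = (1.216 + 0.507)² / 0.1024 = 29.0.
- With continuity correction: (29.0/4)·(1 + √(1 + 4/(29.0·0.32)))² = 35.0 per arm.
- Power at 35 per arm by the same formula is 81.1%. Exact enumeration of the corrected test gives 83.2%.
- Inflation: 70/0.80 = 87.5, so 88.

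All the stated figures reproduce.

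**2. False positives under selective dropout.** The dropout patterns and the 30% rate are assumptions; the documents give no dropout by arm or by outcome. Set-up: 44 children randomised per arm, no true difference, corrected chi-square on children with data, at least 200,000 simulated trials per case. The figure is the chance of a significant result favouring CBT.

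| True rate of losing the diagnosis, both arms | Dropout, CBT | Dropout, comparison | Rates among those remaining | Favouring CBT |
|---|---|---|---|---|
| 30% | 20%, random | 20%, random | 30% vs 30% | 1.3% |
| 30% | 20%, all non-responders | 20%, all non-responders | 37.5% vs 37.5% | 1.4% |
| 30% | 20%, all non-responders | 20%, random | 0.30/0.80 = 37.5% vs 30% | about 6% |
| 30% | 30%, all non-responders | 10%, random | 0.30/0.70 = 43% vs 30% | 14% |
| 10% | 30%, all non-responders | 10%, random | 0.10/0.70 = 14% vs 10% | 3.8% |

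**3. Hiding a real effect.** As an extreme bound, take the planned 42% vs 10% with 20% dropout per arm. Let CBT lose only responders and the comparison arm only non-responders. The rates remaining are (0.42 − 0.20)/0.80 = 27.5% and 0.10/0.80 = 12.5%. Exact power at 35 per arm falls to 25%.

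**4. How firm a typical positive result would be.** Near the planned rates, 15/35 vs 4/35 among those remaining gives p = 0.007. With 9 more children per arm counted as not lost, 15/44 vs 4/44 gives p = 0.010. If 2 of the 9 missing comparison children had in fact lost the diagnosis (15/44 vs 6/44), p = 0.045; if 3 had (15/44 vs 7/44), p = 0.085.

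**5. Counting missing as not lost.**

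- In the 14% case the rates become 30% vs 0.30·0.90 = 27%, and false positives favouring CBT fall to about 3%.
- In the 6% case they become 30% vs 0.30·0.80 = 24%, and the figure stays at 5.8%. The random dropouts in the comparison arm are now wrongly counted as failures, so the rule does not repair this case.
- Power at 42% vs 10% with 20% random dropout: rates become 0.42·0.80 = 33.6% and 0.10·0.80 = 8.0%. Simulated power is 80%, against 83% on children with data. The plan's formula gives 78% at 44 per arm.

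The error rate and power of multiple imputation were not computed.

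**The case against.** The strongest reply is that no completer analysis is written. The plan is silent on the analysis set, and a chi-square is compatible with all randomised children if missing outcomes are counted as not lost. Powering on the expected number with data and inflating to 88 is standard practice. The earlier 19% concerns completion of the protocol, which is not the same as a missing outcome. T2 and T3 are separate from the sessions, and nothing bars a child who stopped sessions from attending. The 20% runs over the whole study, so less may be missing at T2. The two programmes are matched on session number, duration and therapist attention, so the burden is similar. The 14% needs a dropout pattern that no document suggests.

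All of this stands, and it rules out stronger readings. A reader might infer that the plan prescribes testing only the 70 who finish, or excludes 18 of 88 randomised children. It says neither: 88 is the number recruited, and randomisation follows T1. The planned 40 to 45 children per treatment arm do suggest that most of the loss is expected after randomisation. A reader might also infer that the inflation causes the bias, which it does not.

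The reply does not supply a rule. No statement keeps all randomised children in the test, and no provision secures outcomes for those who stop sessions. Matched attendance burden also does not prevent dropout that depends on a child's progress.

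**Conclusion.** The point holds as a gap in the primary analysis with a predictable default: without an all-randomised set or a missing-outcome method, the chi-square will be run on children with data. The sizing is sound.

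How much this matters depends on dropout that cannot be known in advance. Dropout that is random, or equally selective in both arms at 20%, leaves the false-positive rate favouring CBT at about its baseline of 1.3% to 1.4%. Selective dropout in CBT alone at the planned 20% raises it to about 6%, if the true rate is 30% in both arms. The 14% is an extreme case and should not be read as the expected error: with the plan's own 10% comparison rate as the common rate, the same dropout gives about 4%. A large distortion in either direction needs dropout that is strongly selective and differs by arm.

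The change should be made because Hypothesis 1 is the primary claim, about a fifth of the children are expected to drop out, and the remedy is cheap.

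**What to change.** - Make the primary analysis of Hypothesis 1 all randomised children by assigned arm.
- State that children who stop sessions are still invited to the existing T2 and T3 visits.
- Pre-specify multiple imputation of missing diagnoses from arm, T1 ADIS-CSR and CGAS, the diagnosis at the other visit and the parent scales.
- Report two sensitivity analyses at T2 and T3: missing counted as not lost, and an arm-differential (missing-not-at-random) analysis. Both are needed because neither imputation nor missing-as-not-lost fully repairs dropout that depends on the unseen outcome.
- Describe 70 as the expected number with complete data.

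The cost is wording and some extra analysis. Missing-as-not-lost costs about 3 points of power (83% to 80%). Power under the imputation analysis should be checked before the rule is fixed.
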